6. STUDY OBJECTIVES AND ENDPOINTS

6.1 Study Objectives

6.1.1 Primary Objective

The primary objective of this study is to assess the reduction in sUA in patients with gout refractory to conventional treatment treated with two different dose levels of SEL-212 compared to placebo.

6.1.2 Secondary Objectives

The secondary objectives of this study are:

- To compare the pharmacodynamic (PD) effect on sUA in patients with gout refractory to conventional treatment treated with two different dose levels of SEL-212 compared to placebo
- To assess change of the following in patients with gout refractory to conventional treatment treated with two different dose levels of SEL-212 compared to placebo:
 - Tophus burden
 - Patient Reported Outcomes (PROs) including assessments of: patients' quality of life (QoL) (SF-36); activity limitation (HAQ-DI); and Provider Global Assessment of Disease Activity
 - Gout flares
 - Joint tenderness and swelling
- To assess effects on the formation of anti-uricase and anti-pegadricase antibodies
- To assess the safety and tolerability of SEL-212 compared to placebo
- To assess the reduction in serum uric acid (sUA) in patients with gout refractory to conventional treatment treated with two different dose levels of SEL-212 compared to placebo, amongst those with tophi at baseline

6.1.3 Exploratory Objectives

The exploratory objectives of this study are:

- To assess the levels of uricase activity in patients receiving SEL-212 compared to placebo
- To assess the effect on monosodium urate crystal deposits and/or total body monosodium urate crystal uric deposits in patients with gout refractory to conventional treatment treated with two different dose levels of SEL-212 compared to placebo (imaging patients only)
- To assess the status of biomarkers related to inflammation and tolerogenic immunologic responses in patients with gout refractory to conventional treatment treated with two different dose levels of SEL-212 compared to placebo
- To assess the relationship between multiomic markers of gout and treatment effect in patients with gout refractory to conventional treatment treated with SEL-212 compared to placebo
- To assess the impact on patient's self-assessment of gout flares and burden of disease using a validated patient diary (weekly) in patients treated with two different dose levels of SEL-212 compared to placebo

- To assess the correlation between immune tolerance related multiomic markers and anti-pegadricase antibody formation in patients treated with two different dose levels of SEL-212

6.2 Study Endpoints

The confirmatory analysis of efficacy will be performed at Day 28 of Treatment Period 6. Efficacy assessments performed in the extension phase of the study (Treatment Period 7 to Treatment Period 12) will be summarized using descriptive statistics by treatment group only.

6.2.1 Primary Efficacy Endpoint

Each of the two active treatment groups, SEL-212A and SEL-212B, are compared to placebo with regards to the following primary endpoint:

- The percentage of patients who achieve and maintain reduction of sUA < 6 mg/dL for at least 80% of the time during Treatment Period 6 by Day 28.

6.2.2 Secondary Efficacy Endpoints

6.2.2.1 Key Secondary Efficacy Endpoints

Each of the two active treatment groups, SEL-212A and SEL-212B, are compared to placebo with regards to the following key secondary efficacy endpoints:

- Reduction of mean sUA as computed by subtracting the Baseline sUA level from the mean sUA (area under the sUA time curve) during Treatment Period 6
- Percent reduction of mean sUA as computed by subtracting the Baseline sUA level from the mean sUA (area under the sUA time curve) during Treatment Period 6
- The change from Baseline to Day 28 of Treatment Period 6 in the physical summary score of the Short Form Health Survey (SF-36)
- In patients with tophi at Baseline, the percentage of patients with at least partial response (PR) (as best response) in overall tophus response evaluation until Day 28 of Treatment Period 6
- The percentage of patients who achieve and maintain reduction of sUA < 6 mg/dL for at least 80% of the time during Treatment Period 6 in the subset of patients with tophi at baseline
- The change from Baseline to Day 28 of Treatment Period 6 in number of tender joints
- The change from Baseline to Day 28 of Treatment Period 6 in the total score of the Health Assessment Questionnaire (HAQ-DI)
- Gout flare incidence during Treatment Periods 1-6
- Gout flare incidence during Treatment Periods 1-3

6.2.2.2 Additional Secondary Efficacy Endpoints for Double-Blind Treatment Phase

Each of the two active treatment groups, SEL-212A and SEL-212B, are compared to placebo with regards to the following additional secondary efficacy endpoints:

- The percentage of patients who achieve and maintain reduction of sUA < 6 mg/dL for 100% of the time during Treatment Period 6

- Percentage of pre-dose sUA values \leq 6 mg/dL during Treatment Periods 2-6 for each patient
- Pre-treatment anti-pegadricase and anti-uricase antibody formation and levels in each treatment period in the SEL-212 active treatment arms during Treatment Periods 1-6
- The percentage of patients with development of new tophi in the subgroups of tophaceous patients and in non-tophaceous patients at Baseline during Treatment Periods 1-6
- In patients with tophi at Baseline, the percentage of patients with at least PR (as best response) in overall tophus response evaluation until Day 0 of Treatment Period 4
- Change from Baseline to Day 28 of Treatment Period 6 in the subscales of Health Assessment Questionnaire (HAQ-DI), in Provider Global Assessment of Disease Activity, and in subscales of Short Form Health Survey (SF-36)
- The percentage of patients with at least 1 gout flare during Treatment Periods 1-3
- The percentage of patients with at least 1 gout flare during Treatment Periods 1-6
- Change from baseline to Treatment Period 6 in number of swollen joints
- Length of time patients are anti-uricase antibody free or before induction of anti-uricase antibody levels above baseline in patients receiving SEL-212
- Length of time patients are anti-pegadricase antibody free or before induction of anti-pegadricase antibody levels above baseline in patients receiving SEL-212

6.2.3 Exploratory Endpoints for Double-Blind Treatment Phase

The exploratory endpoints of the double-blind Treatment Period of this study are:

- Levels of uricase activity in patients receiving SEL-212
- Levels of monosodium urate crystal deposits and/or total body monosodium urate crystal deposits (imaging patients only)
- Levels of inflammatory and tolerogenic biomarkers
- Changes in antibody production (anti-uricase and anti-pegadricase) in patients in the SEL-212 groups
- Gout flare incidence during Treatment Periods 4-6
- Gout flare incidence during Treatment Periods 1-3 based on self-reported weekly gout flare diary
- Gout flare incidence during Treatment Periods 1-6 based on self-reported weekly gout flare diary
- Gout flare incidence in the Treatment Periods 4-6 based on self-reported weekly gout flare diary
- Assessment of association between multiomic markers of gout and treatment effect in patients treated with SEL-212
- Comparison of immune tolerance related multiomic markers in patients on SEL-212 who developed anti-uricase and anti-pegadricase antibodies vs. those patients on SEL-212 that did not develop anti-uricase and anti-pegadricase antibodies

6.2.4 Exploratory Endpoints for Double-Blind Extension Phase

The exploratory endpoints of the double-blind Extension Period of this study are:

- The change from Baseline to each Treatment Period (7-12) in the extension phase of sUA level
- The change from Baseline to each Treatment Period (7-12) in the extension phase in number of tender joints and number of swollen joints
- In patients with tophi at Baseline, the percentage of patients with at least PR (as best response) in overall tophus response evaluation in each Treatment Period (7-12) in the extension phase
- The change from Baseline to each Treatment Period (7-12) in the extension phase in the total score and in subscales of the Health Assessment Questionnaire (HAQ-DI)
- The change from Baseline to each Treatment Period (7-12) in the extension phase in the summary score and in subscales of the Short Form Health Survey (SF-36)
- Gout flare incidence in Treatment Periods 1-9 and in Treatment Periods 1-12 and percentage of patients with at least one gout flare in Treatment Periods 1-9 and in Treatment Periods 1-12 in the extension phase in the subgroup of patients continued into extension phase
- Number of pre-dose sUA values < 6 mg/dL for each patient stratified by cumulative number of Treatment Periods 7-12 for the subgroup of patients continued into extension phase
- Pre-treatment anti-pegadricase and anti-uricase antibody formation and levels for each treatment period during extension phase in the SEL-212 active treatment arms
- Percentage of patients with development of new tophi in each Treatment Period (7-12) in the extension phase in the subgroups of tophaceous patients and in non tophaceous patients at study baseline (Day 0 Treatment Period 1) and at baseline of extension phase (Day 0 Treatment Period 7)
- Change from baseline to each Treatment Period (7-12) in the extension phase in Provider Global Assessment of Disease Activity
- Length of time patients are anti-uricase antibody free or before induction of anti-uricase antibody levels above baseline in patients receiving SEL-212 in the subgroup of patients continued into extension phase
- Length of time patients are anti-pegadricase antibody free or before induction of anti-pegadricase antibody levels above baseline in patients receiving SEL-212 during extension phase
- Levels of uricase activity in patients receiving SEL-212 during extension phase
- Levels of monosodium urate crystal deposits and/or total body monosodium urate crystal deposits (imaging patients only) during extension phase
- Levels of inflammatory and tolerogenic biomarkers during extension phase
- Changes in antibody production (anti-uricase and anti-pegadricase) in patients in the SEL-212 groups during extension phase
- Assessment of association between multiomic markers of gout and treatment effect in patients treated with SEL-212 during extension phase
- Immune tolerance related multiomic markers in patients on SEL-212 who developed anti-uricase and anti-pegadricase antibodies vs. those patients on SEL-212 that did not develop anti-uricase and anti-pegadricase antibodies

6.2.5 Safety Endpoints

The safety endpoints of this study are:

- Safety and tolerability of SEL-212 compared to placebo as assessed by AEs, AESI, serious AEs (SAEs), deaths, and discontinuations due to AEs
- Additional safety assessments will include review and evaluation of laboratory testing including hematology, coagulation, chemistry, eGFR, urinalysis; UACR, vital signs; immunogenicity analyses; 12-lead ECGs; and physical examination findings.

7. INVESTIGATIONAL PLAN

7.1 Overall Study Design

This is one of two replicate randomized, double-blind, placebo-controlled, parallel-arm trials to determine the safety and efficacy of two different dose levels of SEL-212 compared to placebo. The study will randomize approximately 120 patients with chronic refractory gout. Approximately 60% of the randomized patients will have tophi at Baseline. Patients, stratified as to the presence or absence of tophi, will be randomized in a 1:1:1 allocation ratio prior to Baseline to receive treatment with one of two dose levels of SEL-212 or placebo every 28 days for approximately 6 months in each trial (SEL-212/301 and SEL-212/302). These two trials will have identical designs with respect to being double-blinded, placebo-controlled as well as identical sample sizes, inclusion/exclusion criteria, efficacy/safety assessments and timing thereof, but will be distinguished by the blinded 6-month extension in SEL-212/301 and that SEL-212/302 will include sites outside of the United States. [REDACTED]

[REDACTED] Efficacy assessments will be conducted at intervals that are appropriate to determine treatment effect with samples for the primary endpoint drawn during Treatment Period 6. Samples will be collected at intervals that are appropriate to determine the uricase activity of SEL-212. Safety will be monitored throughout the study with an independent data safety monitoring board (DSMB). After successful completion of the double-blind treatment phase, patients successfully completing six months in SEL-212/301 will continue, in a blinded fashion, to be treated with the identical investigational treatment (one of two dose levels of SEL-212 or placebo) for 6 additional doses, every 28 days, lasting approximately 6 months. This will provide up to 12 months of continuous treatment with SEL-212 in a placebo-controlled fashion.

The study will be divided into 3 study phases: Screening, Treatment, and Follow-up, described below. The study is depicted schematically in [Figure 1](#).

The total duration of participation in the study will range from approximately 50 to 55 weeks (352 to 383 days) as follows:

- Screening and/or washout and premedication Phase: up to 45 days (up to 6.5 weeks)
- Treatment Phase: 168 days (24 weeks)
- Extension Phase: 168 days (24 weeks)
- Safety Follow-Up: 30 days after last infusion

7.1.1 Screening Phase

After providing written informed consent, the patient is considered enrolled in the study. Patients will be evaluated for inclusion during the Screening Phase. For all patients, the standard Screening Phase will be up to 45 days prior to Baseline. The Screening Phase may be initiated by a preliminary screening with an abbreviated informed consent focused on COVID-19 testing and serum uric acid levels followed by providing study-wide informed consent and the remainder of screening assessments if determined to proceed. **Of note**, if the sUA level obtained during preliminary screening meets eligibility requirements

(i.e., ≥ 7 mg/dL), the sUA should **not** be repeated during the subsequent complete screening assessment. Concurrently with the Screening Phase, a premedication period for potential gout flare with colchicine (or non-steroidal anti-inflammatory drug [NSAID], if colchicine is contraindicated) of at least 7 days prior to Baseline will be required for all patients, and a washout period of at least 7 days will be required prior to Baseline for patients on any urate-lowering therapy (ULT). Both the ULT washout period and the gout flare prophylaxis period may be started earlier than 7 days prior to Baseline. At the discretion of the PI, chronic refractory gout patients whose sUA is lower than the eligibility level of ≥ 7 mg/dL on prescreening or initial screen, may undergo ULT washout prior to retesting the sUA. Initiation of gout flare prophylaxis with colchicine (or non-steroidal anti-inflammatory drug [NSAID], if colchicine is contraindicated) can also be considered coincidentally with the ULT washout to prevent a potential gout flare.

7.1.2 Double Blind Treatment Phase

The total duration of the double-blind Treatment Phase will be approximately 6 months (i.e., 168 days, consisting of six 28-day treatment cycles).

Eligible patients, stratified as to the presence or absence of tophi, will be randomized in a 1:1:1 allocation ratio prior to baseline to receive one of two dose levels of SEL-212 or placebo. The SEL-212 doses will differ as to the SEL-110.36 component. Participants will receive SEL-037 administered at a dose level of 0.2 mg/kg via intravenous (IV) infusion immediately after receiving SEL-110.36 at a dose level of either 0.1 mg/kg (SEL-212A) or 0.15 mg/kg (SEL-212B) via IV infusion. The placebo will consist of normal saline that will be administered in the same way that the SEL-212 components are administered to maintain the integrity of the study blind. Refer to [Section 10](#) for details about study drug administration.

Patients will complete 6 treatment periods each having a duration of 28 days. Patients will receive treatment with study drug or placebo on Day 0 of each treatment period for a total of 6 doses. For each treatment cycle, participants will receive premedication to minimize the potential for infusion reactions during study drug administration. After completing the study drug infusions, participants will remain at the investigational site for 1 hour for safety assessments.

With each dose, a blood sample will be drawn for assessment of sUA level and uricase activity immediately prior to infusion (i.e., Time 0 h) with SEL-212 or placebo and 1 hour after the infusion of the second component of SEL-212 or of placebo is completed. Serum uric acid will be assessed through additional post-infusion blood samples at pre-determined time points by an independent, central, unblinded medical monitor.

Gout flares will be assessed at each study visit during the Treatment Phase using a validated definition of flares in patients with established gout ([Gaffo 2018](#)). In addition, in an exploratory manner, gout flares will be self-assessed by the patient weekly after randomization and in each Treatment Period using a weekly flare diary ([Poiley 2016](#)). Health Questionnaires, tophus burden and joint swelling and tenderness will be assessed on Day 0 of Treatment Periods 1 and 4, and at the end of Treatment Period

6 or early termination (ET) if a patient discontinues the study prior to the end of 6 monthly infusions. Samples for anti-uricase, anti-PEG, and anti-pegadricase antibody levels will be taken (i) prior to administration of study drug dosing and at Day 21 for each of the six treatment periods throughout the trial and (ii) at the end of Treatment Period 6 or at ET. Exploratory assessments of inflammatory/immunologic biomarkers and multiomic analysis will also be assessed.

Safety laboratory samples, consisting of, but not limited to, complete blood count (CBC) including white blood cell count (WBC) and absolute neutrophil count; liver function tests (LFTs) including aspartate aminotransferase (AST) and alanine transaminase (ALT); serum lipids (including triglycerides and low density lipoprotein (LDL)), analyses of renal function including creatinine, urine albumin creatinine ratio (UACR), and estimated glomerular filtration rate (eGFR) will be collected on Day 0 and Day 21 of Treatment Period 1, on Day 21 only of each of Treatment Periods 2-5, and on Day 21 and Day 28 / ET of Treatment Period 6. On Treatment Period 1 Day 0, safety laboratory samples will be collected pre-infusion in both the SEL-212 arm and the placebo arm. Concomitant medications and procedures and adverse events (AEs) will be monitored continuously during the study. Post-Baseline chest X-rays (CXR) will be taken at six months and one year / ET to assess for presence of or changes in interstitial lung disease (ILD) compared to baseline CXR.

[figure not shown]
7.1.3 Follow-Up Phase

Patients will be followed for safety monitoring (30 + 4 days) after their final study drug infusion and will have an End of Study visit by telephone at the following times: either (1) at completion of the Extension Phase or (2) at early termination if the patient voluntarily withdraws consent. Patients who terminate the study prematurely will continue to be followed by having all Early Termination assessments performed. Patients who terminate the study prematurely who are unable to be on-site for the Early Termination visit will be contacted by telephone for safety follow-up.

If withdrawn from study drug, regardless of reason, the patient will continue study visits to the end of Treatment Period 12.

7.1.4 Double-Blind Extension Phase

Patients will enroll in a double-blind extension to begin after the conclusion of Treatment Period 6. Patients in any cohort who have met the stopping rule during the blinded treatment phase will continue study visits in the extension phase without study drug administration. All SEL-212 patients in the extension phase will receive up to an additional 6 monthly doses of SEL-212 at the same dose level as during the Treatment Phase for those that maintain Day 21 sUA <6 mg/dL. Patients who meet the stopping rule during the extension phase will be withdrawn from study drug and will continue study visits to the end of the extension phase.

Figure 1: Study Schematic

7.2 Number of Patients

The study will randomize approximately 120 patients with chronic refractory gout. Approximately 60% of the randomized patients will have tophi at Baseline

7.3 Treatment Assignment

Patients will be randomized in a double-blind way with an allocation ratio of 1:1:1 to receive treatment with two different dose levels of SEL-212 or placebo. Randomization will be stratified by presence/absence of tophi.

7.4 Dose Adjustment Criteria

Unless otherwise specified, study drug will be administered as described in [Section 9](#) and [Section 10](#).

7.4.1 Safety Criteria for Adjustment or Stopping Doses

7.4.1.1 SEL-212 or Placebo

A patient will be withdrawn from study drug for meeting the following stopping rule:

- sUA level < 2.0 mg/dL, measured 1 hour after the infusion of the second component of study drug is completed during Treatment Period 1
- AND
- sUA level > 1.0 mg/dL measured at the Day 21 visit of Treatment Period 1 or sUA level > 6.0 mg/dL at the Day 21 visit of any of Treatment Periods 2-11

Stopping rules will be assessed by an independent, central, unblinded medical monitor.

If withdrawn from study drug during the double-blind treatment period (Treatment Period 1 to 6) or the double-blind extension period (Treatment Period 7 to 12), regardless of reason, the patient will continue study visits to the end of Treatment Period 12.

The window for all Day 21 visits is +2/-1 days. If a Day 21 visit sUA value drawn within the protocol window is not available, but if a sUA value drawn at an unscheduled visit after the Day 21 window is available prior to dosing that is ≤ 1.0 mg/dL during Treatment Period 1 or ≤ 6.0 mg/dL during Treatment Periods 2-11, the patient will not be required to be withdrawn from study drug and will be eligible to receive their subsequent dose.

If 1) a Day 21 visit sUA value drawn within the protocol window is not available and no subsequent sUA results are available or 2) a Day 21 visit sUA value drawn within the protocol window is not available and

a subsequent sUA drawn at an unscheduled visit after the Day 21 window is > 1.0 mg/dL during Treatment Period 1 or > 6.0 mg/dL during Treatment Periods 2-11, then the patient will be withdrawn from study drug based on the protocol deviation. If a protocol deviation occurs where a patient is not able to be dosed within the dosing day window (for example in the case of COVID-19 restrictions temporarily preventing dosing) the current treatment period will be extended up to a maximum of 90 days without skipping doses for patients with a Day 21 visit sUA value ≤ 1.0 mg/dL during Treatment Period 1 or ≤ 6.0 mg/dL during Treatment Periods 2-11 in the D21 visit window or subsequent up to the rescheduled dosing visit. If this protocol deviation occurs such that the patient was unable to be dosed within the dosing day window for the Treatment Period 7 Day 0 dose, then the Treatment Period 6 Day 28 visit should still occur 28 days (+3/-4 days) after the Treatment Period 6 dose or as close to the visit window as possible to collect the final primary endpoint sUA sample. In this specific instance, the dosing day Treatment Period 7 Day 0 should then occur as soon as possible afterward up to a maximum of 90 days from the preceding dose.

To maintain the blind, a central group of unblinded pre-specified medical personnel will adjudicate the implementation of the stopping rules.

If withdrawn from study drug, the patient will continue study visits to the end of Treatment Period 12. At the discretion of the Investigator, the patient will be permitted to return to ULT 60 days after the patient's last study drug treatment. ULT shall not be SEL-212 or any experimental or marketed uricase (e.g., rasburicase (Elitek, Fasturtec), pegloticase (Krystexxa®), for the remainder of the study.

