Prescribing Information 2014). While its use is associated with improvements in musculoskeletal function, quality of life, and pain, only approximately 42% of patients maintain a target serum urate level less than 6 mg/dL after 6 months of the approved dose regimen of 8 mg once every 2 weeks. The vast majority of patients (89%) develop anti-pegloticase antibodies (*Lipsky 2014*). High titer antibodies appear to adversely affect the pharmacokinetics and pharmacodynamics of the enzyme and are associated with a decrease in therapeutic response and increased risk of infusion reactions. Approximately 26% of patients taking Krystexxa® report infusion reactions, 6.5% experience anaphylaxis, and the incidence of infusion reactions correlate with high anti-pegloticase antibody titer (*Sundy 2011*). These adverse events are typically preceded by a loss of urate-lowering effects.

In addition to infusion reactions and gout flares, the most common adverse reactions with Krystexxa® are nausea, contusion, nasopharyngitis, constipation, chest pain, anaphylaxis, and vomiting. In the 2 pivotal trials, there were 4 reported cases of exacerbations of pre-existing congestive heart failure in subjects receiving Krystexxa® every 2 weeks.

The high rate of treatment failure and the potential for anaphylactic reactions are potential drawbacks of Krystexxa® since its approval.

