10. STUDY DRUG MATERIALS AND MANAGEMENT

10.1 Study Drug

This is a randomized, double-blind study. The designated site representative (e.g., pharmacist) will be unblinded to enable preparation of study drug on the day of treatment. The site representative will take appropriate steps during study drug preparation to maintain the integrity of the study blind. Prior to study drug administration in Treatment Periods 2 through 12, the unblinded medical monitor will determine a patient's eligibility for treatment with study drug by evaluating the patient's sUA level measured from the blood sample obtained from Day 21 of the prior treatment period.

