3. Treatment Period 6 only. Treatment Period 6 Day 28 assessment will be used for Treatment Period 7 Day 0 pre-dose assessment. Do not repeat sample collection on Treatment Period 7 Day 0.
4. Premedication to minimize potential infusion reactions: oral antihistamines at 12 (± 2) hours and 2 (± 1) hours and IV steroids at 1 (± 0.5) hours prior to study drug.
5. Obtain sample prior to study drug infusion.
6. Obtain sample 1 hour (+15/-0 min) after completion of infusion of Component 2. If a patient is withdrawn from study drug, the post-dose uricase activity and post-dose sUA samples do not need to be collected.
7. Component 1 will be SEL-110.36 at 0.1 mg/kg for patients randomized to treatment with SEL-212A and SEL-110.36 at 0.15 mg/kg for patients randomized to SEL-212B or will be placebo for patients randomized to placebo.
8. Before starting infusion with Component 2, a period of up to approximately 30 minutes is permitted after completion of infusion of Component 1.
9. Component 2 will be SEL-037 for patients randomized to treatment with either SEL-212A or to SEL-212B or will be placebo for patients randomized to placebo.

PHASE 3 STUDY: SEL-212/301
VERSION: 6.1

EFFECTIVE DATE

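### The stopping rule's TP1 1-hour condition conflicts with the extension-dosing text and the missing-Day-21 fallback, so one SEL-212 patient gets different dosing answers

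*Protocol*

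**What the plan says.** **The rule.** Protocol 7.4.1.1, with copies in the synopsis and SAP 3.3, sets out two bullets joined by AND. The first is "sUA level < 2.0 mg/dL, measured 1 hour after the infusion of the second component of study drug is completed during Treatment Period 1". The second holds both Day 21 limits. In the first period the limit is passed by any value above 1.0 mg/dL. After that the wording is "sUA level > 6.0 mg/dL at the Day 21 visit of any of Treatment Periods 2-11". The first condition is read once, in Treatment Period (TP) 1. The second is read at each Day 21 visit.

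**The fallback.** The paragraphs that follow in 7.4.1.1 cover a Day 21 sample not drawn in its window. If a later unscheduled sUA is above the same limit, or if there is no later sUA, "then the patient will be withdrawn from study drug based on the protocol deviation". The 1-hour value is not mentioned.

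**The extension.** Protocol 7.1.4 (also the synopsis and SAP 3.3) provides up to 6 more doses for SEL-212 patients "for those that maintain Day 21 sUA <6 mg/dL". Again there is no 1-hour condition.

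**Other mentions.** Protocol 10.1, and 9.4 in nearly the same words, has the unblinded medical monitor "determine a patient's eligibility for treatment with study drug by evaluating the patient's sUA level measured from the blood sample obtained from Day 21". SAP 9.3.3 gives the stopping-rule level as Day 21 cut-offs only. Appendix B, footnote 6, times the 1-hour draw: "Obtain sample 1 hour (+15/-0 min) after completion of infusion of Component 2". No passage says what happens if that TP1 sample is missed or unusable.

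**The concern.** The single TP1 1-hour reading gates every later Day 21 check under the rule. A SEL-212 patient at 2.0 mg/dL or above on that reading does not meet the rule, however high a later in-window Day 21 value is. Two other provisions reach the opposite result for the same patient. One is in the same section as the rule and the other governs the extension.

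Three things are at stake.

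- **Dosing.** The rule sits under the heading for safety criteria. Protocol 5.5 says of infusion reactions with the marketed uricase: "These adverse events are typically preceded by a loss of urate-lowering effects". Whether a patient who has lost response is infused again should not depend on which paragraph the adjudicator reads.
- **Equal handling.** Two SEL-212 patients with the same lost response are treated differently because of one early sample, or because a Day 21 draw was late.
- **The estimand.** SAP 6.1 makes meeting the stopping criteria a composite failure. Protocol 13.4.1 uses discontinuation for lack of efficacy, which only includes meeting the criteria. An exempt patient whose drug is stopped through the fallback could be a failure under one wording and fall under treatment policy in the other. The stopping-rule summaries in SAP 8.1 and 10.1 need the same single definition.

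**Working it through.** **The plan's own figure.** The only related figure is the sample size. The inputs in protocol 13.1 are 45% vs 5%, two-sided 2.5%, 90% power and a continuity correction. The uncorrected n is (2.2414·√(2·0.25·0.75) + 1.2816·√(0.45·0.55 + 0.05·0.95))² / 0.40² = 26.75. The corrected n is (26.75/4)·(1 + √(1 + 4/(26.75·0.40)))² = 31.6, so 32 per arm. Then 32/0.92 = 34.8, so 35 per arm and 105 in total. This matches the plan, and nothing below enters it.

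**Logic of the rule.** Let A = TP1 1-hour sUA < 2.0, B = TP1 Day 21 > 1.0 and C = any TP2-11 Day 21 > 6.0 (mg/dL). As laid out, the patient stops if A AND (B OR C). The table applies the three texts to the same patients. The fallback column assumes the same value came from a late sample.

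| Patient | Rule, in-window Day 21 | Fallback, late sample | 7.1.4 extension doses |
|---|---|---|---|
| SEL-212, 1-hour 0.5, later 8.0 | stopped | stopped | no |
| SEL-212, 1-hour exactly 2.0, later 8.0 | **not stopped** | stopped | no |
| SEL-212, 1-hour 2.5, later 8.0 | **not stopped** | stopped | no |
| SEL-212, 1-hour missing, later 8.0 | not stated | stopped | no |
| Placebo, always 8.0 | not stopped | stopped | not addressed |
| SEL-212, sustained 0.5 | not stopped | not stopped | yes |

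The second and third rows are the contradiction. The alternative parse, (A AND B) OR C, would remove it. But B and C share a bullet under the AND, and that parse would also stop the placebo patient.

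**Further infusions after a TP2 Day 21 value above 6 mg/dL.** If 7.1.4 governs the extension: TP3 to TP6 = 4. If only the rule applies: TP3 to TP12 = 10.

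**How many patients.** The documents give no rate, so this range is an assumption. Suppose 1-5% of about 80 SEL-212 patients (40 + 40) lack a TP1 1-hour value below 2.0 mg/dL.

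- Without the value: 80 × 0.01 = 0.8 to 80 × 0.05 = 4 patients. The chance of at least one is 1 − 0.99^80 = 55% to 1 − 0.95^80 = 98%.
- The gap matters only if the patient later loses response. With the plan's non-response of 1 − 0.45 = 0.55 as a rough proxy: 0.8 × 0.55 = 0.44 to 4 × 0.55 = 2.2 patients. The chance of at least one is 1 − 0.9945^80 = 36% to 1 − 0.9725^80 = 89%.

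**Effect on the primary variable.** A patient with sUA persistently above 6 mg/dL in TP6 fails the 80% criterion with or without the stopping rule. A difference arises mainly for a TP1 Day 21 value above 1.0 and up to 6.0 mg/dL. With a 1-hour value below 2.0, that patient is stopped and counted as a failure. With 2.0 or higher, the patient continues and may be a TP6 responder.

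**The case against.** The rule is worded alike in three places, so it looks deliberate. The 1-hour condition plausibly keeps placebo patients on blinded infusions, because without it almost all of them would be withdrawn. The documents do not state this purpose, but it is the sensible reading. It explains why the condition exists. It does not settle a SEL-212 patient at 2.0 mg/dL or above, and 7.1.4 is addressed to SEL-212 patients specifically.

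The 7.1.4 sentence could be shorthand, since its paragraph also refers to the stopping rule. The fallback could be a separate route, since it rests on a protocol deviation. Both readings are possible. Neither is stated, and the outcomes still differ for the same sUA.

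Several stronger readings are tempting, and the documents do not support them:

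- **That 9.4 and 10.1 decide dosing on Day 21 sUA alone.** They give no threshold and do not say alone. They cover placebo patients too and may simply summarise the rule's Day 21 step, as may SAP 9.3.3.
- **That the exemption lasts the whole trial.** Section 7.1.4 and the fallback can each end dosing. The exemption is from the rule proper at in-window visits.
- **That a missing 1-hour sample exempts the patient.** The documents are silent. That the rule is then not met is an inference from its wording.
- **That lost response is left without safeguards.** Protocol 10.7 withdraws patients after Grade 3 or 4 infusion reactions, a DSMB reviews safety, and unblinded personnel adjudicate the rule. The remark in 5.5 concerns another product.

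Infusions are observed and patients stay for 1 hour afterwards, so a missed sample need not be common.

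**Conclusion.** The contradiction stands in a narrow form. For a SEL-212 patient with a TP1 1-hour sUA of 2.0 mg/dL or higher, the rule in 7.4.1.1 gives one answer, and its own fallback and 7.1.4 give another. This follows from the text and needs no assumed rate.

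The number affected is probably small and limited to patients who later lose response. Under the assumed 1-5%, and the 55% non-response proxy, it is about 0.4 to 2.2 patients. The exposure at issue is up to 4 further infusions after a TP2 Day 21 value above 6 mg/dL if 7.1.4 governs the extension, and up to 10 if it does not.

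A reader might infer that the primary result is distorted. The likely effect is small, and no power or sample-size figure moves. The point is still worth settling because it bears on a safety stopping criterion and on who counts as a stopping-rule failure.

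**What to change.** Reconcile 7.4.1.1, including its fallback paragraphs and the copies in the synopsis and SAP 3.3, with 7.1.4, 9.4 and 10.1. All of them should give one result for a SEL-212 patient whose TP1 1-hour sUA is 2.0 mg/dL or higher, and one for a patient whose TP1 1-hour sample is missing. The choice of rule belongs to the sponsor's clinicians. This review takes no view on it.

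Then align the stopping-criteria event in SAP 6.1 and the lack-of-efficacy event in protocol 13.4.1 with the reconciled wording, so that the same patients are composite failures under both. The level described in SAP 9.3.3 should match.

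The cost is a protocol clarification and matching SAP text. The medical monitor is already unblinded and already reviews Day 21 values, and the 1-hour sample is already scheduled, so no procedure is added.
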